#### **5.2** Dose Optimization

[figure not shown]
In order to determine the optimal dose of MB-102, Group 1 subjects may receive different doses of Investigational Product (IP). The maximum dose of 4 µmol/kg has already been tested in 8 subjects in a prior clinical study (Pilot 1B) and found to be safe and well tolerated.

Coefficient of Variation (CV) will be used as the criterion for selecting dose. CV is defined here as the standard deviation divided by the mean (expressed as a percentage) of the time constants from multiple single exponential fits to the trans-cutaneous fluorescence emission decay over non-overlapping 15 minute time windows between 2 and 4 hours after IP dosing. The CVs will

be separately averaged across 2 subjects within FS I, II and III skin color types and 2 subjects within FS IV, V, and VI skin color types.

The initial dose will be 4  $\mu$ mol/kg, and the target CV will be 5%. Dose de-escalation will only be performed if the resulting average CVs for both skin type groups are below the maximum stated requirements. As shown in **Figure 1**, the CV thresholds for dose de-escalation from 4 to 3  $\mu$ mol/kg, 3 to 2  $\mu$ mol/kg, and 2 to 1  $\mu$ mol/kg are 4.3%, 4.1%, 3.5%, respectively. These dose scaling targets assume that the CV has a square root dependence on the signal size (i.e. "Poisson" noise distribution), but after dose de-escalation, a second CV determination will be made to ensure the target CV of 5% has been achieved. Details on the methods and analysis of dose selection will be available in a separate MediBeacon Experimental Protocol.

Figure 1 Dose Optimization Schema

#### 5.2.1 Group 2 Dosing

Subjects enrolled in Group 2 will receive a dose of 4 µmol/kg of MB-102. No dose optimization work will be conducted.

#### 5.2.2 Group 3 Dosing

Subjects enrolled in Group 3, Cohorts 5, 6, SOG and part of the SeVG group will receive a dose of 4 µmol/kg of MB-102. No dose optimization work will be conducted.

A subset of SeVG subjects (up to 20 subjects who weigh greater than 110 lbs [50 kg]) and all subjects in cohorts 7 and 8 will receive a fixed dose of 7 mL (130 mg). This dose is equivalent to what a 191 lb subject would receive if dosed at the standard 4 µmol/kg dose level. This dose change is within the safety margin of previously performed non-clinical studies. The purpose of testing a fixed dose level is to determine if such a dose will be adequate across a variety of subject weights and still remain an accurate measurement of tGFR. A fixed dose level would simplify dose preparation when the product goes to market.

A subset of subjects enrolled into Cohort 7 will receive 2 doses of MB-102 (both doses will at the fixed dose level of 7 mL or 130 mg). The 2nd dose of MB-102 will be administered either 12 hours or 24 hours (Cohort 7B) after the first dose.

#### 5.3 Overview of Study Procedures

### **5.3.1** Groups 1 and 2

Potential subjects will be screened for eligibility within 40 days prior to planned dosing. Following pre-dose procedures to ensure eligibility, two ORFM sensors will be affixed to the subjects in Groups 1 and 2; one on the sternum (all subjects) and a second one on an alternative location which may include the forehead, occipital triangle, pectoralis major, lower hip, upper hip, lower sternum or chin. The subject will then receive MB-102 and iohexol injections. MB-102 will be administered by IV injection over 30 seconds, followed by a 10 mL saline flush IV over 30 seconds. Iohexol will be administered to each subject following the MB-102 administration by IV injection over 30 seconds, followed by a 10 mL saline flush IV over 30 seconds.

PK sampling will be collected pre-dose and at 5, 10, 15, 30, 60, 90, 120, 180, 240, 300, 360, 480, 600 and 720 minutes post-dose.

For the subgroup in Cohort 4 who consent to have extended PK collection, additional PK samples will occur at 960 (16 hours), 1440 minutes (24 hours), 1920 minutes (32 hours), 2400 minutes (40 hours) and 2880 minutes (48 hours) post-dose.

Urine will be collected pre-dose and for the 12 hour duration of PK sampling (and extended out to 48 hours for subjects in the extended PK subgroup) for all subjects in Groups 1 and 2. Aliquots of urine will be collected during each void, and the total volume excreted during the 12 or 48 hour post-dose period will be recorded.

Safety assessments in the form of clinical labs, vital signs, ECGs and adverse event collection will occur during the dosing day.

Within 7 +/- 3 days of dosing, subjects will return to the study center for additional safety follow-up assessments.

#### 5.3.2 Group 3

Potential subjects will be screened for eligibility within 40 days prior to planned dosing. Following pre-dose procedures to ensure eligibility, one ORFM sensor will be affixed to the subject and (in certain subjects) a  $2^{nd}$  sensor (connected to a separate device) may be attached to a  $2^{nd}$  location. Sensor placement locations include: the sternum, the forehead, occipital triangle (side of neck), pectoralis major, lower hip, upper hip, lower sternum or chin. A dose of 4  $\mu$ mol/kg MB-102 will be administered by IV injection over 30 seconds, followed by a 10 mL saline flush IV over 30 seconds.

PK sampling in cohort 5 will be collected pre-dose and at 5, 10, 15, 30, 60, 90, 120, 180, 240, 300, 360, and 480 minutes post-dose (8 hour collection period).

PK sampling in cohorts 6, 7 (single dose subjects), the SOG cohort, SeVG-1 and SeVG-2 will be collected pre-dose and at 5, 10, 15, 30, 60, 90, 120, 180, 240, 300, 360, 480, 600 and 720 minutes post-dose (12 hour collection period).

PK sampling in cohort 7 [including 7A and 7B] (multiple dose subjects) will be collected at the following timepoints: pre-dose and 5, ( $\pm 1$  min), 120, 180, 240, 300 ( $\pm 5$  min), 360, 480 and 600 ( $\pm 10$  min). In addition, a PK sample will be drawn at 720 minutes after the first dose administered in Cohort 7B. Prior to the 2nd dose, a pre-second dose draw will be performed. Blood draws will re-start after the administration of the 2nd dose and be collected at the following timepoints: 5 ( $\pm 1$  min), 120, 180, 240, 300 ( $\pm 5$  min), 360, 480, and 600 ( $\pm 10$  min). It is anticipated that this subset of subjects will remain at the study center for 24 – 36+ hours. As of Amendment 11, PK sampling for multiple dose subjects will have an additional PK blood draw at 60 minutes ( $\pm 5$  min).

PK sampling in cohort 8, and 8A will be collected pre-dose and at 5, 10, 15, 30, 60, 90, 120, 180, 240, 300, 360, 480, 600, 720 minutes (12 hours); 960 (16 hours), 1440 (24 hours), 1920 (32 hours), 2400 (40 hours) and 2880 minutes (48 hours).

PK sampling in cohort 8B will be collected at collected pre-dose and at 5, 10, 15, 30, 60, 90, 120, 180, 240, 300, 360, 480, 600, 720 minutes (12 hours); 960 (16 hours), and 1440 (24 hours).

Urine will not be collected in Group 3.

Safety assessments in the form of clinical labs, vital signs, ECGs and adverse event collection will occur during the dosing day.

Prior to sensor placement, and each time a sensor is removed (or a sensor replaced) melanin and erythema will be measured using a Mexameter® MX18. Photographs of the sensor once affixed to a subject may also be taken in order to assess the utility of the adhesive. No subject identifying features will be included in the photographs.

Within 7 +/- 3 days of dosing, subjects will return to the study center for additional safety follow-up assessments.

#### 5.4 Discussion of Study Design

This pilot study is designed to provide safety and pharmacokinetic data as well as ORFM data that will be used for the design of future studies.

#### 5.5 Selection of Study Population

#### 5.5.1 Number of Planned Subjects

Up to 261 subjects divided into 3 enrollment Groups with normal or impaired renal function who meet all of the eligibility criteria will be enrolled. An effort will be made to ensure both men and women are enrolled across all cohorts.

No sample size calculation was made to determine the number of planned subjects. This is a hypothesis generating study to optimize the device and algorithm and is not intended to meet statistical significance for this purpose.

#### 5.5.2 Inclusion Criteria

To be eligible for study entry, all subjects must satisfy all of the following criteria:

#### Main Criteria for Inclusion (Group 1 and Group 2):

- Age  $\geq$  22 years male or female
  - Eligible female non-pregnant subjects who are either not of child-bearing potential or willing to use adequate contraception during the trial
  - Males must be willing to practice abstinence or utilize adequate contraception from dosing day to at least 7 days post dose
- Subjects willing to comply with study requirements
- Subjects who have signed an informed consent form
- Normal or non-clinically significant screening and baseline 12 lead ECG in the opinion of the PI
- Adequate venous access sufficient to allow blood sampling per protocol requirements

#### Main Criteria for Inclusion (Group 3):

- Age  $\geq$  18 years male or female
  - Eligible female non-pregnant subjects who are either not of child-bearing potential or willing to use adequate contraception during the trial
  - o Males must be willing to practice abstinence or utilize adequate contraception from dosing day to at least 7 days post dose

- Subjects willing to comply with study requirements
- Subjects who have signed an informed consent form
- Normal or non-clinically significant screening and baseline 12 lead ECG in the opinion of the PI
- Adequate venous access sufficient to allow blood sampling per protocol requirements

# Group 1 Cohort 1 (30 subjects), Group 2 Cohort 3 (20 subjects) and Group 3: Cohorts 5 (8 subjects), SOG Cohort (up to 27 subjects), SeVG-1 (up to 25 subjects) and Cohort 7 (up to 16 subjects)

- Are healthy as determined by medical history, with no clinically significant findings on screening and baseline physical exams, vital signs and clinical laboratory panels or conditions that could adversely impact the subject's participation or safety, conduct of the study or interfere with study assessments
- Have eGFR (CKD-EPI equation) of ≥60 ml/min/1.73m² (normal to Stage 2 CKD) at the time of screening

Approximately half of the patients enrolled in each cohort will have Fitzpatrick Scale Type I, II or III skin color type and the other half will have Fitzpatrick scale Type IV, V or VI skin color type.

#### Group 1 Cohort 2 (30 subjects)

- Possess stable renal function in the opinion of the PI
- Have eGFR (CKD-EPI equation) of 15 59 mL/min/1.73m^2 at the time of screening
- Stable use of immunosuppressant medications (when applicable)
- ~15 subjects per cohort to have Fitzpatrick Type I, II or III skin color type
- ~15 subjects per cohort to have Fitzpatrick Type IV, V or VI skin color type

# Group 2 Cohort 4 (40 subjects) and Group 3 Cohorts 6 (8 subjects), SeVG-2 (up to 25 subjects) and Cohort 8 (up to 16 subjects)

- Possess stable renal function as defined as the most recent historical (within 3 months) eGFR and screening eGFR differing by ≤20%.
- Have eGFR (CKD-EPI equation) of <59 mL/min/1.73m^2 based on a historical value collected within 3 months or from the screening serum creatinine
- Stable use of immunosuppressant medications (when applicable) defined as no changes in the last 30 days or expected through the follow up visits, and a prednisone dose of <20 mg/day (or another steroid's equivalent dose) (see Section 5.10.2 and Table 3).

Approximately half of the subjects per Cohort to have Fitzpatrick Type I, II or III skin color type Approximately half of the subjects per Cohort to have Fitzpatrick Type IV, V or VI skin color type.

#### 5.5.3 Main Criteria for Exclusion (Group 1):

• Women who are pregnant, lactating or planning to become pregnant during the study, or women who are of childbearing potential unwilling to use a barrier method of birth

control

- Intolerant to venipuncture
- Recent donation or loss of blood or plasma: 100 mL to 499 mL within 30 days prior to the initial dose of the study medication; or more than 499 mL within 56 days prior to the initial dose of study medication
- Participation in another interventional trial within 30 days of screening or concurrently enrolled in any other medical research study which could impact the results of the study
- History of drug or alcohol abuse within the past year
- History of allergy or hypersensitivity to MB-102 or iohexol, or other related (iodinated contrast media) products, or any of the inactive ingredients
- History of skin sensitivity to adhesives (e.g. Band-Aids, surgical tape)
- Any food allergy, intolerance, restriction or special diet that, in the opinion of the Principal Investigator, could contraindicate the subject's participation in this study
- Subjects who have allergies to 2 or more classes of drugs. (*Intolerance to a drug is not considered a drug allergy*)
- Stable use (no changes within 30 days) of prescription or OTC medications
- NSAID use within 2 days of dosing day
- History of coagulation disorders or bleeding disorders that in the judgement of the investigator places the subject at undue risks for study related procedures
- Are homozygous for sickle cell disease
- Have a known thyroid disorder
- Have pheochromocytoma
- Currently on Coumadin (warfarin) who have an INR>4 at Screening
- Current history of AIDS or HIV
- Hepatitis B antigen positive, or C antibody positive
- Site personnel immediately associated with the study or their immediate family members
- Any characteristics which, in the opinion of the investigator, makes the subject a poor candidate for participation in the clinical trial
- Prior enrollment and dosing in this Pilot 2 study
- Significant scaring, tattoos or alterations in pigmentation on the sternum that would alter sensor readings versus other areas of the skin

#### Additional Exclusion: Group 1 Cohort 1:

- Any other serious or uncontrolled medical disorder, active infection, physical exam finding, laboratory finding, altered medical exam or psychiatric condition that in the opinion of the investigator would limit the subjects' ability to complete study requirements or increase risk to the subject or interpretability of the study results.
- Note: history of gallstones or kidney stones are not excluded so long as the condition is not acute within 30 days of dosing.

#### Additional Exclusion: Group 1 Cohort 2

- Stage 5 CKD at the time of screening
- Recent (within 3 months) significant medical condition or surgical procedure including myocardial infarction, laparoscopic procedures, or other medical inventions
- Doses of prednisone greater than 10 mg/day within the last 90 days

### 5.5.4 Main Criteria for Exclusion: (Group 2)

- Women who are pregnant, lactating or planning to become pregnant during the study, or women who are of childbearing potential unwilling to use a barrier method of birth control
  - o Males must be willing to practice abstinence or utilize adequate contraception from dosing day to at least 7 days post dose
- Unable to have venous access placed in both arms
- Recent donation or loss of blood or plasma: 100 mL to 499 mL within 30 days prior to the initial dose of the study medication; or more than 499 mL within 56 days prior to the initial dose of study medication
- Participation in another interventional trial within 30 days of treatment or concurrently enrolled in any other medical research study which could impact the results of the study
- History of drug or alcohol abuse within the past year
- History of skin sensitivity to adhesives (e.g. Band-Aids, surgical tape)
- History of severe allergic hypersensitivity reactions (unacceptable adverse events) or anaphylactoid reaction to any allergen including drugs, MB-102, iohexol or other related (iodinated contrast media) products (*Intolerance to a drug is not considered a drug allergy*)
- NSAID use within 2 days of dosing day
- History of coagulation disorders or bleeding disorders that in the judgement of the investigator places the subject at undue risks for study related procedures
- Are homozygous for sickle cell disease
- Have hyperthyroidism or current thyroid cancer
- Have pheochromocytoma
- Currently on Coumadin (warfarin) who have an INR>4 at Screening
- Current history of AIDS or HIV
- Current evidence of an active Hepatitis B or C infection. (If the subject is Hepatitis C antibody positive, but the Hepatitis C RNA is below the level of detection, they are considered immune and may be eligible).
- Site personnel immediately associated with the study or their immediate family members
- Any characteristics which, in the opinion of the investigator, makes the subject a poor candidate for participation in the clinical trial
- Prior exposure to MB-102
- Significant scarring, tattoos or alterations in pigmentation on the sternum that would alter sensor readings versus other areas of the skin

#### 5.5.5 Main Criteria for Exclusion: (Group 3)

 Women who are pregnant, lactating or planning to become pregnant during the study, or women who are of childbearing potential unwilling to use a barrier method of birth control

- Males must be willing to practice abstinence or utilize adequate contraception from dosing day to at least 7 days post dose
- Unable to have venous access
- Recent donation or loss of blood or plasma: 100 mL to 499 mL within 30 days prior to the initial dose of the study medication; or more than 499 mL within 56 days prior to the initial dose of study medication
- Participation in another interventional trial within 30 days of treatment or concurrently enrolled in any other medical research study which could impact the results of the study
- History of drug or alcohol abuse within the past year
- History of skin sensitivity to adhesives (e.g. Band-Aids, surgical tape)
- History of severe allergic hypersensitivity reactions (unacceptable adverse events) or anaphylactoid reaction to any allergen including drugs, and MB-102 (*Intolerance to a drug is not considered a drug allergy*)
- NSAID use within 2 days of dosing day
- History of coagulation disorders or bleeding disorders that in the judgement of the investigator places the subject at undue risks for study related procedures
- Currently on Coumadin (warfarin) who have an INR>4 at Screening
- Current history of AIDS or HIV
- Current evidence of an active Hepatitis B or C infection. (If the subject is Hepatitis C antibody positive, but the Hepatitis C RNA is below the level of detection, they are considered immune and may be eligible).
- Site personnel immediately associated with the study or their immediate family members
- Any characteristics which, in the opinion of the investigator, makes the subject a poor candidate for participation in the clinical trial
- Significant scarring, tattoos or alterations in pigmentation on the sternum that would alter sensor readings versus other areas of the skin

# Additional Exclusion: Group 2 Cohort 3 and Group 3 Cohorts 5, SOG Cohort, SeVG-1 and Cohort 7

- History of significant cardiovascular disease, heart failure, myocardial infarction in the past 3 months, or NYHA class 3 or 4 HF
- Any other serious or uncontrolled medical disorder, active infection, physical exam finding, laboratory finding, or psychiatric condition that in the opinion of the investigator would limit the subjects' ability to complete study requirements or may put the subject at increased risk or compromise interpretability of study results. *Note: a history of gallstones or kidney stones are not excluded so long as the condition is not acute within 30 days of dosing.*

Sites enrolling subjects into Cohort 7 (multiple dose group only for Protocol Versions 11.0 and 12.0) should strive to recruit subjects with a baseline eGFR > 90 ml/min/1.73 $m^2$  if feasible. The intent to enroll more normal subjects is to ensure clearance of MB-102 prior to the second dose in order to establish re-dose timelines for future subjects. In addition, subjects enrolled into the subsets of cohort 7 and 8 (Protocol Version 12.0) should strive to enroll subjects at the extremes of the Fitzpatrick Skin Scale (I and II and V and VI). Finally, subjects enrolled into Cohort 7A

and 7B will an eGFR between 90 and 120 ml/min/1.73 $m^2$ . In addition, subjects in Cohort 7B will have a 24 hour period between doses (for a total post dose follow-up period of 36 + hours).

#### Additional Exclusion: Group 2 Cohort 4 and Group 3 Cohorts 6, SeVG-2, and 8

- Recent (within 3 months) significant medical condition or surgical procedure including myocardial infarction, thoracic laparoscopic procedures, or other significant medical inventions
- Received >20 mg/day of prednisone or an equivalent dose of glucocorticoid for more than 7 days in the last 90 days prior to dosing day for an acute or chronic disorder
- Currently receiving dialysis
- Currently anuric

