
- Cohort 5: 8 subjects with normal to CKD stage 2 renal function,
- **Cohort 6**: 8 subjects with impaired renal function [CKD stage 3-5]. Fluorescence will be measured by the Brilliance ORFM Device and algorithm optimization will be performed.

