#### Main Criteria for Exclusion: (Group 3)

- Women who are pregnant, lactating or planning to become pregnant during the study, or women who are of childbearing potential unwilling to use a barrier method of birth control
  - Males must be unwilling to practice abstinence or utilize adequate contraception from dosing day to at least 7 days post dose
- Unable to have venous access
- Recent donation or loss of blood or plasma: 100 mL to 499 mL within 30 days prior to the initial dose of the study medication; or more than 499 mL within 56 days prior to the initial dose of study medication
- Participation in another interventional trial within 30 days of dosing or concurrently enrolled in any other medical research study which could impact the results of the study
- History of drug or alcohol abuse within the past year
- History of skin sensitivity to adhesives (e.g. Band-Aids, surgical tape)
- History of severe allergic hypersensitivity reactions (unacceptable adverse events) or anaphylactoid reaction to any allergen including drugs, or MB-102 (*intolerance to a drug is not considered a drug allergy*).
- NSAID use within 2 days of dosing day
- History of coagulation disorders or bleeding disorders that in the judgement of the investigator places the subject at undue risks for study related procedures
- Currently on Coumadin (warfarin) who have an INR>4 at Screening
- Current history of AIDS or HIV
- Current evidence of an active Hepatitis B or C infection. *If the subject is Hepatitis C antibody positive, but the hepatitis C RNA is below the level of detection, they are considered immune and are be eligible for enrollment.*
- Site personnel immediately associated with the study or their immediate family members
- Any characteristics which, in the opinion of the investigator, makes the subject a poor candidate for participation in the clinical trial
- Significant scaring, tattoos or alterations in pigmentation on the sternum that would alter sensor readings versus other areas of the skin

Additional Exclusion: Group 2 Cohort 3, and Group 3 Cohorts 5, SOG, SeVG-1 and Cohort 7

	History of significant cardiovascular disease, heart failure, myocardial infarction in the past 3 months, or NYHA class III or IV HF

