#### **Group 3:** Up to 141 subjects to be enrolled:

- Cohort 5: 8 subjects to have normal to CKD Stage 2 renal function
- Cohort 6: 8 subjects with impaired renal function (CKD stage 3-5)
- Sensor Optimization Group (SOG): 18 subjects with normal to CKD Stage 2 renal function; if optimization still requires additional work; a third and final group of 9 subjects will be enrolled to finalize the device and algorithm design.
- Sensor Validation Group (SeVG): up to 50 subjects will be enrolled who have normal renal function to Stage 5 CKD. A subset of subjects (approximately 20) who weigh greater than 110 lbs (50 kg) will receive a fixed dose of 7 mL (130 mg). Subjects receiving the fixed dose may be normal or renally compromised.

A study interim analysis will be performed after completion of the SeVG cohort of all previously collected subject data (Groups 1, 2 and 3 through the SevG enrollment). This analysis will be performed to summarize clinical data in support of pivotal product development and regulatory submissions. It is not the intention to stop the study early or revamp sample size for the remaining cohorts.

The final algorithm and sensor will be further tested in up to 48 additional subjects:

- Cohort 7: up to 24 subjects to have normal to CKD Stage 2 renal function
  - A subset of cohort 7 subjects will have 2 doses of MB-102; the 2nd dose of MB-102 will be administered 12 hours after the first dose (original Cohort 7, 7A)
  - A subset of subjects (Cohort 7B) will have 2 doses of MB-102; the 2nd dose of MB-102 will be administered 24 hours after the first dose
- Cohort 8: up to 24 subjects with impaired renal function (CKD stage 3-5) and followed for 24-48 hours
- All cohort 7 and 8 subjects will receive the fixed dose of 130 mg (7 mL).

Cohorts 7 and 8 will be divided into the following subsets in order to test additional sensor types in development. These subsets are outlined in **Table 2**.

Cohort	Dosing	Follow-up (Hrs)	Sensors	Enrollment
Subgroups				
Cohort 7	Single or 2 doses	12 - 24 hours	Brilliance (1-2 sensors/subject)	Up to 24
Cohort 7A	Single or 2 doses	12 - 24 hours	Brilliance (1-2 sensors/subject) and Brilliance 2-part sensor	subjects
Cohort 7B	2 doses	36 hours	Brilliance (1-2 sensors/subject) and Brilliance 2-part sensor	
Cohort 8	Single dose	48 hours	Brilliance (1-2 sensors/subject)	Up to 16
Cohort 8A	Single dose	48 hours	Brilliance (1-2 sensors/subject) and Brilliance 2-part sensor	subjects

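### Group 3 lacks the prior-dosing exclusion used in Groups 1 and 2, so people whose data tuned the sensor or algorithm may re-enter as test subjects and be counted again in overall safety totals

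*Combined protocol and SAP*

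**What the plan says.** The three groups have separate exclusion lists. Group 1 (section 5.5.3) excludes "Prior enrollment and dosing in this Pilot 2 study". Group 2 (section 5.5.4) excludes "Prior exposure to MB-102". The Group 3 list (section 5.5.5) has no such item. Its closest criterion is "Participation in another interventional trial within 30 days of treatment", together with concurrent enrolment in other research that could affect the results. The synopsis list for Group 3 has the same gap and again names only other trials: "Participation in another interventional trial within 30 days of dosing".

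Group 3 holds both development and test cohorts. For Cohorts 5 and 6 the synopsis says that "algorithm optimization will be performed", and the Sensor Optimization Group (SOG) exists to refine the sensor further. The SeVG is there to validate the Brilliance sensor. Section 5.1 then states: "The final algorithm and sensor will be further tested in up to 48 additional subjects"; these are Cohorts 7 and 8. The Group 3 primary endpoint is that transdermal GFR matches plasma GFR.

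Section 9.1.1 defines the Safety Analysis Set as consented, dosed subjects. Neither it nor the other analysis sections says how to handle a person dosed in more than one cohort. The synopsis plans adverse event summaries by cohort and overall.

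**The concern.** Sites apply eligibility text as written. Cohort 5, SOG, SeVG-1 and Cohort 7 share one set of renal and health criteria, and Cohorts 6, SeVG-2 and 8 share another. A person who qualified for a tuning cohort would therefore broadly qualify for a later test cohort.

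Two things are at stake. First, the protocol treats skin colour as relevant to the readout, and section 9.1.3.1 says that the conversion to GFR may use volume of distribution and body surface area. These are largely stable features of a person. Agreement in someone whose data helped to set the conversion may be better than agreement in a new person. Labelling whole cohorts as development or test does not remove that overlap.

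Second, overall exposure counts and subject-based adverse event rates are sums over cohorts. They equal numbers of distinct people only if nobody repeats.

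**Working it through.** **1. The eligibility texts side by side.**

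| Criterion | Group 1 (5.5.3) | Group 2 (5.5.4) | Group 3 (5.5.5) |
|---|---|---|---|
| Earlier dosing | Earlier Pilot 2 dosing barred | Any earlier MB-102 barred | No item |
| Other trials, 30 days | Yes | Yes | Yes |

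Group 2 carries the other-trials item as well as the prior-exposure item, so the former is not a substitute for the latter. The Group 3 inclusion criteria, the cohort-specific exclusions and the replacement rule (5.5.7) supply no equivalent.

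**2. Whether another Group 3 item closes the gap.** The blood-loss criterion covers "100 mL to 499 mL within 30 days prior to the initial dose of the study medication". Section 8.4 gives about 135 mL drawn on a standard dosing day, which falls in that band, so a repeat is delayed by about 30 days but not barred. The investigator-discretion item does not mention earlier exposure. Group 3 also drops the sickle cell, thyroid and pheochromocytoma items. These match iohexol label warnings, and Group 3 receives no iohexol. That reasoning does not explain dropping an MB-102 item, and the protocol gives no other reason.

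**3. The plan's own figures.**
- Planned Group 3: 8 + 8 + 27 + 50 + 48 = 141. Planned total: 60 + 60 + 141 = 261.
- Exposed to date in Pilot 2 (8.1): 120 + 70 + 12 = 202. Adverse event rate: 22/202 = 10.9%, as stated.
- Brilliance tuning pool: 8 + 8 + 18 = 34, up to 8 + 8 + 27 = 43. With the 120 from Groups 1 and 2, whose data also fed the algorithm, it is 154 to 163.

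All stated totals reproduce. The arithmetic is additive and correct.

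**4. Illustration for Cohorts 7 and 8.** Let r be the share of the 48 Cohort 7 and 8 subjects who were already in an earlier Group 3 cohort. The documents give no value; r = 10% to 40% is an assumption.
- Test subjects not previously used: 48 × (1 − r).
- Distinct people in Group 3: 141 − 48r. Distinct people overall: 261 − 48r.
- Approximate 95% upper bound with zero events: 3/n.

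| r | Not previously used | Distinct, Group 3 | 3/n, Group 3 | Distinct, overall | 3/n, overall |
|---|---|---|---|---|---|
| 0% | 48 | 141 | 2.1% | 261 | 1.15% |
| 10% | 43.2 | 136.2 | 2.2% | 256.2 | 1.17% |
| 25% | 36 | 129 | 2.3% | 249 | 1.20% |
| 40% | 28.8 | 121.8 | 2.5% | 241.8 | 1.24% |

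If the repeats came from Groups 1 or 2 instead, the Group 3 count would stay at 141 and only the overall count would fall.

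**5. Effect on the reported rate.** If k of the 202 were repeat entries (k is also an assumption) and the 22 people with events were all different, the rate would be 22/(202 − k): 22/192 = 11.5% at k = 10 and 22/154 = 14.3% at k = 48. The value 48 is the SeVG number implied by 202 − 120 − 8 − 8 − 18. If some of the 22 were the same person, the rate would be lower.

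**The case against.** The strongest reply is that a missing exclusion is not a plan to re-use people. The protocol speaks of additional subjects for Cohorts 7 and 8 and reports subjects exposed, and subjects can be read as unique persons. This stands as far as it goes: a reader might infer that repeat enrolment took place, or that the published totals are wrong, and the documents support neither. They leave the matter open.

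Second, the conversion is common to all subjects, not fitted person by person. Cohorts 7 and 8 use a fixed dose, whereas Cohorts 5, 6 and SOG were dosed by weight, and Groups 1 and 2 used other prototypes. This also stands. It limits the likely leakage and means that no amount can be derived.

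Third, the upper end of the assumed range is strained. If repeats split evenly, 40% of the 24 Cohort 8 places is about 10 people, but Cohort 6, the only impaired-function Brilliance tuning cohort, has 8. The rest would have to come from SeVG-2, which is described as verification, or from Groups 1 and 2. Cohorts 7A and 7B are further limited to an eGFR of 90 to 120.

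Fourth, the study is described as hypothesis-generating, has no sample size calculation, and will be followed by pivotal studies. That lowers the stakes but does not remove them: the interim summary supports discussions about the pivotal trial, and Cohorts 7 and 8 are meant to test the final algorithm.

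**Conclusion.** The gap in the text is real and appears in both the synopsis and the body. It permits overlap between tuning and test people, and repeat counting in overall safety totals. Adverse event rates by cohort are not affected, because a person who enters two cohorts counts once in each. The two earlier exclusions also differ in scope: Group 1 bars earlier Pilot 2 dosing only, and Group 2 bars any MB-102.

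Two stronger readings should be resisted. A reader might infer that repeats cut the number of independent observations in Cohorts 7 and 8 from 48 to 29. A tuning subject who appears once among the 48 is still independent of the other 47; what is lost is separation from the tuning data. A reader might also apply r to all 141 Group 3 subjects and obtain 3/n bounds of 2.4%, 2.8% and 3.5%. That would require the same repeat share in Cohorts 5, 6, SOG and SeVG, whereas r is defined on the 48. The bounds that follow are 2.2%, 2.3% and 2.5% against 2.1%.

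The safety effect is therefore small over the assumed range. The agreement effect is unknown in size and, if present, optimistic. The case for acting is that the safeguard already exists in the Group 2 list and is cheap.

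**What to change.** For remaining Cohort 7 and 8 enrolment, add the Group 2 item "Prior exposure to MB-102" to the Group 3 exclusions, in both section 5.5.5 and the synopsis.

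For Group 3 subjects already enrolled:
- Add an identifier that links a person across cohorts, including Groups 1 and 2, and report how many people repeat.
- Base the SeVG and Cohort 7 and 8 agreement summaries on people not used in tuning, with the result including repeats shown as a sensitivity summary.
- Report overall safety by unique persons and by number of exposures.

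The cost is one eligibility line, one linkage variable and one extra summary. The downside is slightly slower recruitment or a few fewer test-set subjects. If linkage finds no repeats, the existing totals stand as counts of distinct people.
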